4.2 Endpoints

4.2.1 Primary endpoint

- Incidence of adverse events, including injection site reactions from first administration of trial product to end of the trial period (53 weeks including follow-up)

4.2.2 Secondary endpoints

4.2.2.1 Supportive secondary endpoints

Key supportive secondary endpoints prospectively selected for disclosure (e.g. clinicaltrials.gov and EudraCT) are marked with an asterisk (*).

- Supportive secondary efficacy endpoints
 - Change from baseline (randomisation) to end of treatment period (52 weeks) in:
 - cross-sectional total adipose tissue compartments (TAT)*,
 - subcutaneous adipose tissue compartments (SAT)*, and
 - intra-abdominal or visceral adipose tissue compartments (VAT)*determined by quantitative computed tomography (CT) scans
 - Change from baseline (randomisation) to end of treatment period (52 weeks) in Treatment Satisfaction Questionnaire for Medication (TSQM-9) scores for:
 - effectiveness*
 - convenience*
 - global satisfaction*
- Supportive secondary safety endpoints
 - Change from baseline to the end of treatment period (52 weeks) in:
 - Physical examination
 - Body weight
 - Vital signs
 - Electrocardiogram (ECG)
 - Clinical laboratory test results including haematology, biochemistry, fasting glucose, fasting insulin, steady state beta cell function (%B) and insulin resistance (IR) (HOMA estimates), and HbA1c levels
 - Occurrence of anti-somapacitan antibodies for subjects randomised to somapacitan from randomisation to end of the trial period (53 weeks including follow-up)*
 - Occurrence of anti-hGH antibodies for subjects randomised to Norditropin[®] FlexPro[®] from randomisation to end of the trial period (53 weeks including follow-up)
 - Incidence of clinical technical complaints

5 Trial design

5.1 Type of trial

This is a multicentre, national, randomised, open labelled, parallel-group, active controlled trial to compare safety of once weekly somapacitan with daily Norditropin[®] FlexPro[®] in previously hGH treated Japanese GHD subjects for 52 weeks. (20 weeks dose titration, 32 weeks fixed dose treatment) followed by 1 week washout.

[figure not shown]

Figure 5–1 Trial design

Sixty (60) subjects will be randomised in a 3:1 (somapacitan : Norditropin[®] FlexPro[®]) ratio to receive somapacitan (approximately 45 subjects) or Norditropin[®] FlexPro[®] (approximately 15 subjects) during a 52 weeks period (20 weeks dose titration followed by 32 weeks fixed dose treatment). The randomisation will be stratified according to sex (male and female). Discontinued subjects will not be replaced.

5.2 Rationale for trial design

The inclusion of the active controlled arm in the open-labelled design is to compare safety including local tolerability (i.e. injection site reactions) of somapacitan to daily Norditropin[®] FlexPro[®] treatment. The open-labelled design is chosen because a blinded design would not be technically feasible due to the difference in injection frequency, and in order to be able to compare the degree of subject satisfaction related to daily vs. weekly injections, which would not be possible if a double-dummy design was applied.

Trial NN8640-4043 showed that at baseline and during the titration period, the number of patients with IGF-I standard deviation score (SDS) below -2 was different in the somapacitan group than in the Norditropin[®] FlexPro[®] group. Based on these data, the following will be implemented:

1. Addition of an inclusion criteria ensuring that only patients with IGF-I levels between -2 SDS and +2 SDS will be included.
2. Addition of one titration visit, allowing up to five opportunities for dose adjustments.

No positive test results for anti-somapacitan antibodies or anti-hGH antibodies were reported in trial NN8640-4043. Therefore, antibody samplings will be performed only at randomisation and at the final follow-up visit.

The somapacitan PK modelling results from trial NN8640-4043 showed steady state from 2 weeks and forward following initial dose as well as following each dose adjustment, allowing a titration schedule in alignment with normal clinical practise and facilitating patient recruitment.

The treatment period is 52 weeks, consisting of a 20 week titration period and a 32 week fixed dose period. Two washout periods are included for measurement of antibodies; before treatment start and following last treatment, as hGH or somapacitan in serum may cause false negative results in antibody assays. First washout is at randomisation where sampling for antibodies must take place minimum 12 hours after last dose of daily hGH. Second washout period is at end of trial, where samplings for antibodies are taken at the follow-up visit (week 53). Because IGF-I is a biomarker of hGH mediated effect, IGF-I has been chosen as a titration marker. An individualised dose titration regime rather than a fixed body weight based regime will be used. Clinical studies have shown that adverse effects were less frequent in subjects receiving dose-titration compared to weight based dosing, and current clinical practice for hGH treatment in AGHD is individual dose titration^{19, 20}. The suggested titration period allows for five opportunities to adjust the dose of somapacitan or Norditropin[®] FlexPro[®] to achieve an optimal targeted serum IGF-I concentration.

5.3 Treatment of subjects

Time of injections:

- Somapacitan subjects will inject themselves once a week s.c. in the morning no later than 10 AM to ensure consistency of PK/PD with previous trials. On site visit days this can be extended until 12 PM (noon). Trial drug may not be administered in the morning before relevant visit procedures have been performed (see section 2).
- Norditropin[®] FlexPro[®] subjects will inject themselves daily s.c. in the evening (to reflect standard treatment practice) throughout the trial and only in the morning (no later than 12 PM (noon) and at least 12 hours after injection the evening before) during observed trial drug administration. Injections with Norditropin[®] FlexPro[®] the night before blood sampling for anti-hGH antibodies must occur at least 12 hours prior to sampling.

The first dose will be administered by the subject on Day 0 (at randomisation). The first dose will be fixed, and will be provided by the electronic case report form (eCRF). The last dose will be

administered by the subject at home, for subjects in the somapacitan treatment arm prior to the visit at week 51+4 days and for subjects in the Norditropin[®] FlexPro[®] arm 3 times after that visit (so that Norditropin[®] FlexPro[®] will be administered 7 times in week 51). No trial drug will be administered in Week 52 prior to the follow-up visit. The maximal treatment duration for a single subject is 52 weeks.

Subjects in both arms will be trained in the use of the pen-injector and inject themselves with trial drug under the supervision of the site staff at the visits where administration is observed, and will inject themselves at home.

5.3.1 Dose titration

During the first 20 weeks the dose will be titrated every fourth week starting from week 4. The last dose adjustment will be done at week 20. This allows five opportunities for dose adjustment (weeks 4, 8, 12, 16 and 20). Dose titration is based on insulin-like growth factor-I standard deviation score (IGF-I SDS) values used for calculation of the next dose. The dose adjustment calculations will provide the new doses for the subjects in the eCRF. IGF-I, insulin-like growth factor binding protein – 3 (IGFBP-3) and IGF-I SDS results will not be made available to the investigator during the trial.

The dose administered to the subject must be entered in the IWRS.

Subjects will come to the clinic 3 weeks and 3 days after the previous dose adjustment visit for an IGF-I, IGFBP-3 and PK blood sample draw. Handling deviations from this schedule is described in section [5.3.5](#). The dose adjustments are performed at weeks 4, 8, 12, 16 and 20, i.e. four days after the IGF-I titration samples have been collected. Dose adjustments will be provided over the phone, except for the last dose adjustment (week 20) which will happen at site. After last dose adjustment visit (week 20), the individual dose level is fixed.

Besides the IGF-I based dose adjustment during the titration period, dose reduction can be considered during the entire trial period (including the titration period) at the investigator's discretion for safety concerns. If adverse events with a probable relationship to the trial drug are persistent but continuation in the trial is acceptable, as judged by the investigator and subject, dose reduction in steps of 25% can be considered. If, after consecutive dose reduction steps, AEs still persist, the subject's treatment may be discontinued or the subject may withdraw as described in section [6.4](#) and [6.5](#).

If a subject reports symptoms of GH related AEs at a dose adjustment visit, the dose titration in the eCRF should be performed prior to potentially reducing the dose by 25% (performing the dose reduction in the eCRF), as the IGF-I based titration might reduce the dose.

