5.3.3 Titration for subjects treated with somapacitan

The fixed starting dose of somapacitan at randomisation visit (Day 0) are described in [Table 5–1](#), dose titration in [Table 5–2](#). The starting doses were tested to be safe in NN8640-3947 and are expected to be below the ideal maintenance dose for IGF-I SDS target for most subjects.

Table 5–1 Starting doses for somapacitan subjects

Group	Starting dose of somapacitan*	Starting dose converted to daily exposure
Subjects between 18 and 60 years of age	1.5 mg/week	0.214 mg/day
Females on oral oestrogen irrespective of age	2.0 mg/week	0.286 mg/day
Subjects older than 60 years	1.0 mg/week	0.143 mg/day

*The starting doses are expected to be below the ideal maintenance dose for IGF-I SDS target for most subjects. Individual adjustment of dose based on individual IGF-I response will be performed during the first 20 weeks.

Table 5–2 Dose Titration Algorithm for somapacitan subjects

IGF-I SDS Interval (3 weeks and 3 days after last dose adjustment)	Increment/reduction of weekly dose
IGF-I SDS > 3	-1 mg
$2 < \text{IGF-I SDS} \leq 3$	-0.5 mg
$0 < \text{IGF-I SDS} \leq 2$	-
$-2 < \text{IGF-I SDS} \leq 0$	+0.7 mg
IGF-I SDS ≤ -2	+1.5 mg

If the algorithm returns a dose of less than 0.1 mg, the weekly dose of somapacitan must be 0.1 mg. Hence, the minimum weekly dose of somapacitan is 0.1 mg. The maximum weekly dose of somapacitan is 8 mg. If the dose is larger than 4 mg, the dose should be split into two injections of equal size.

If somapacitan subjects forget or are unable to inject the dose in the morning, they have to take the drug as soon as possible during the same day. If the subjects have failed to inject the trial product on the planned dosing day in the titration period, they should contact the trial site since the following IGF-I visit will have to be rescheduled, i.e. postponed two weeks (see section 5.3.5). Injections should remain in the body areas of thighs and/or abdomen with rotation within these body areas for every injection.

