5.3.4 Titration for subjects treated with daily Norditropin® FlexPro®

The fixed starting dose of Norditropin® FlexPro® given daily from randomisation visit (Day 0) is described in [Table 5–3](#), dose titration in [Table 5–4](#).

Table 5–3 Starting doses for Norditropin® FlexPro® subjects

Group	Starting dose of Norditropin® FlexPro®*
Subjects between 18 and 60 years of age	0.2 mg/day
Females on oral oestrogen irrespective of age	0.3 mg/day
Subjects older than 60 years	0.1 mg/day

*The starting doses are expected to be below the ideal maintenance dose for IGF-I SDS target for most subjects. Individual adjustment of dose based on individual IGF-I response will be performed during the first 20 weeks.

Table 5–4 Dose Titration Algorithm for Norditropin® FlexPro® subjects

IGF-I SDS Interval (3 weeks and 3 days after last dose adjustment)	Increment/reduction of daily dose
IGF-I SDS > 3	-0.1 mg/day
$2 < \text{IGF-I SDS} \leq 3$	-0.05 mg/day
$0 < \text{IGF-I SDS} \leq 2$	-
$-2 < \text{IGF-I SDS} \leq 0$	+0.1 mg/day
IGF-I SDS ≤ -2	+0.2 mg/day

If the algorithm returns a dose of less than 0.05 mg, the daily dose of Norditropin® FlexPro® must be 0.05 mg. Hence, the minimum daily dose of Norditropin® FlexPro® is 0.05 mg. The maximum daily dose of Norditropin® FlexPro® is 1.0 mg.

If Norditropin® FlexPro® subjects forget or are unable to inject the dose in the evening they should skip the dose and continue on the next evening with the next scheduled dose. If a subject failed to inject the trial product the evening before a planned IGF-I visit in the titration period, the subject should contact the trial site since the IGF-I visit will have to be rescheduled, i.e. postponed two weeks. Injections should only be performed in the thighs and/or abdomen with rotation within these body areas for every injection.

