5.3.5 Deviations from titration schedule

The dose titration schedule in the protocol should be followed in order to allow titration to an optimal therapeutic dose for all subjects. Five dose adjustment evaluations are required for optimal dose titration.

If for any reason a subject cannot be dose titrated on a scheduled dose adjustment day (e.g.: IGF-I value not available, subject comes for IGF-I sampling in a non-fasting state, or subject has not taken the dose as prescribed),

- the **previous IGF-I sampling** will be repeated or rescheduled to two weeks later
- the **affected dose adjustment** will be rescheduled to two weeks later

Consecutive postponements are not allowed, i.e. no visit may be rescheduled more than once.

Changes to the dose titration like those described above and dose reduction in steps of 25% will not be considered protocol deviations. Reasons for dose reduction should be entered in the eCRF. Based on this information it may be decided to ask for additional information regarding the deviation (see section [14](#)). If the answer explains the deviation no further action will be taken.

[figure not shown]

Figure 5–2 Flow of rescheduling visits in the titration period

If a subject has not completed at least 3 dose adjustment evaluations, this will be considered a protocol deviation because fewer than three completed dose adjustment evaluations are not expected to be sufficient to achieve therapeutic doses in a majority of subjects. Trial visits after week 20 will not be postponed.

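### Titrating before an elected 25% AE-driven reduction, with no rule to withhold an up-titration, can leave low doses, including every starting dose, the same or higher when IGF-I SDS is 0 or below

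*Combined protocol and SAP*

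**What the plan says.** Section 5.3.1 of the protocol sets two dose mechanisms side by side. One is the IGF-I algorithm at weeks 4, 8, 12, 16 and 20. The other is a discretionary 25% reduction for safety, available throughout the trial. Where they meet, at an adjustment visit in a subject with GH-related symptoms, the instruction is that "the dose titration in the eCRF should be performed prior to potentially reducing the dose by 25" per cent. The only reason given is "as the IGF-I based titration might reduce the dose".

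The algorithm works in both directions. Table 5–2 (column "Increment/reduction of weekly dose") adds 0.7 mg when IGF-I SDS is above −2 and at most 0, and 1.5 mg when it is −2 or below. Table 5–4 (column "Increment/reduction of daily dose") adds 0.1 or 0.2 mg/day in the same bands. Nothing in sections 5.3.1 to 5.3.5 suspends the increase when a reduction is elected.

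Other relevant text:
- Section 5.3.3 says that starting doses "are expected to be below the ideal maintenance dose for IGF-I SDS target for most subjects".
- Section 5.3.1 says that "IGF-I SDS results will not be made available to the investigator during the trial", although the resulting dose appears in the eCRF.
- Section 5.5 justifies 25% as the smallest step thought likely to make a real difference to GH-related AEs.

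**The concern.** Safety is the primary objective, and the 25% step is the protocol's dose tool for a subject who has GH-related AEs but can continue. The order rule guards against one interaction, a double reduction, and leaves the opposite one open. A fixed increment is large relative to a low dose, so a proportional cut taken afterwards may not undo it. The investigator would then have chosen a reduction while the subject goes home on the same dose or a higher one. Early increases are foreseen, since starting doses are set below maintenance for most subjects. At stake is whether an elected step does what section 5.5 intends. No test or estimate in section 17 depends on it.

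**Working it through.** **Inputs.** Starting doses are 1.0, 1.5 and 2.0 mg/week (Table 5–1) and 0.1, 0.2 and 0.3 mg/day (Table 5–3). Increments are +0.7 or +1.5 mg/week (Table 5–2) and +0.1 or +0.2 mg/day (Table 5–4). Maximum doses are 8 mg/week and 1.0 mg/day. The plan gives no figure of its own to reproduce.

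**Formula.** With current dose d and increment inc, one step as written gives 0.75 × (d + inc). This is at least d when 0.75 × inc ≥ 0.25 × d, that is, when d ≤ 3 × inc.
- Somapacitan: 3 × 0.7 = 2.1 mg/week; 3 × 1.5 = 4.5 mg/week.
- Norditropin: 3 × 0.1 = 0.3 mg/day; 3 × 0.2 = 0.6 mg/day.

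The highest starting doses are 2.0 mg/week and 0.3 mg/day, so all six fall within the limits. The maximum doses bind only well above these limits and do not change them. Above a limit the dose falls, but by less than 25% unless the maximum absorbs the increase.

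**Week 4, small increment.**
- Somapacitan: 0.75 × 1.7 = 1.275 (+27.5%); 0.75 × 2.2 = 1.65 (+10%); 0.75 × 2.7 = 2.025 (+1.25%, practically unchanged).
- Norditropin: 0.75 × 0.2 = 0.15 (+50%); 0.75 × 0.3 = 0.225 (+12.5%); 0.75 × 0.4 = 0.30 (unchanged).

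**Week 4, large increment.** Somapacitan becomes 1.875, 2.25 and 2.625 mg/week (+87.5%, +50%, +31.25%). Norditropin becomes 0.225, 0.30 and 0.375 mg/day (+125%, +50%, +25%).

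**Later visits.** The table assumes a small increase at every visit and one step elected only at the visit shown. Entries are the net change from the current dose, by starting dose.

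| Week | Somapacitan 1.0 / 1.5 / 2.0 | Norditropin 0.1 / 0.2 / 0.3 |
|---|---|---|
| 4 | +27.5% / +10% / +1.3% | +50% / +12.5% / 0% |
| 8 | +5.9% / −1.1% / −5.6% | +12.5% / 0% / −6.2% |
| 12 | −3.1% / −6.9% / −9.6% | 0% / −6.2% / −10.0% |
| 16 | −8.1% / −10.4% / −12.2% | −6.2% / −10.0% / −12.5% |
| 20 | −11.2% / −12.8% / −14.1% | −10.0% / −12.5% / −14.3% |

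On this one hypothetical path the dose is the same or higher in 10 of 30 cells. Three of the ten are exactly 0%, and none falls at week 16 or 20. This is not a frequency.

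**Two steps at week 4**, 0.5625 × (d + inc). With the small increment the results are 0.956, 1.2375 and 1.519 mg/week, and 0.1125, 0.169 and 0.225 mg/day. Five of the six starting doses fall; Norditropin 0.1 does not. With the large increment the two lower starting doses in each arm still end higher.

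**Order reversed**, 0.75 × d + inc. With the small increment: 1.45, 1.825 and 2.2 mg/week, and 0.175, 0.25 and 0.325 mg/day, all higher than under the current order.

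**Rounding.** Pen increments are not stated. If they are 0.1 mg for somapacitan and 0.05 mg for Norditropin (assumption), rounding the small-increment week-4 results down gives 1.2, 1.6 and 2.0 mg/week, and 0.15, 0.20 and 0.30 mg/day. All six are still the same or higher; three are exactly unchanged (2.0, 0.20 and 0.30).

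**The case against.** The strongest defence is that the order is deliberate and the investigator is not trapped. The titrated dose is on screen before the decision to reduce. Further steps are expected ("If, after consecutive dose reduction steps, AEs still persist" introduces what follows only after several), and section 5.3.5 adds that "dose reduction in steps of 25% will not be considered protocol deviations". Section 6.4 requires treatment to stop for symptoms that the subject or investigator finds unacceptable. The general criterion for 25% steps in section 5.3.1 is a persistent AE with a probable relationship to trial drug. Starting doses set below maintenance make early increases likely, but they do not make them likely in combination with such AEs. All of this stands and limits the consequences. It does not correct the rule: a single step can still fail to lower the dose, and the safeguards depend on someone noticing.

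The defence also has a fair point about the remedy. Section 5.2 reports an arm difference in subjects below −2 SDS in trial NN8640-4043 and adds a titration visit in response. Withholding increases works against that aim, and at week 20 the effect lasts. Withholding also gives one discretionary decision in an open-label trial more influence over dose. These are real costs, though confined to symptomatic subjects for whom a reduction has already been chosen.

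Stronger readings are tempting but unsupported. A reader might infer that the order itself is the error, but reversing it gives higher doses; the gap is the missing rule on increases. A reader might infer that AE-driven reductions fail generally, but with SDS above 0 and up to 2 the step is a full 25% cut, and above the limits the dose falls. A reader might also infer harm to subjects or a biased safety comparison between arms, but the documents give no way to compute how often the situation arises or what follows.

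**Conclusion.** The point holds as an inexpensive improvement to the design. At an adjustment visit with IGF-I SDS of 0 or below, one elected 25% step leaves any dose up to 2.1 or 4.5 mg/week, or 0.3 or 0.6 mg/day, the same or higher. On starting doses with the small increment the net effect runs from 0% to +50%, contrary to the purpose stated in section 5.5. The problem lies mainly at weeks 4–12 in subjects still on low doses. At week 20, no net cut with the small increment needs a subject still at or below 2.1 mg/week or 0.3 mg/day, for example after four no-change results. That is a special case.

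The conclusion rests on reading sections 5.3.1 to 5.3.5 as containing no hold rule, on a single elected step, and on exact doses before rounding; the rounding check does not change it.

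**What to change.** Add to section 5.3.1, and match in the eCRF dose logic:

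> If the investigator elects an AE-driven reduction at a dose adjustment visit and the IGF-I algorithm returns an increase, the increase is not applied at that visit and the 25% reduction is taken from the current dose, rounded to the nearest deliverable dose that does not exceed the current dose; a subject already at the minimum dose stays at the minimum dose. Otherwise proceed as written.

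Before rounding, starting doses become 0.75, 1.125 and 1.5 mg/week, and 0.075, 0.15 and 0.225 mg/day. If the Norditropin pen moves in 0.05 mg steps (assumption), 0.075 lies midway between 0.05 and 0.10, so the sponsor should say which applies.

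The cost is a short protocol addition, identical in both arms, and a small eCRF update with testing. No visits, samples or subjects are added. The clinical downside is slower up-titration and possibly lower IGF-I in these symptomatic subjects, including any at SDS −2 or below. Before rounding and below the maximum dose, the new dose is lower than under the current text by 0.75 × inc: 0.525 or 1.125 mg/week, or 0.075 or 0.15 mg/day.

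At week 20 that gap carries through the 32-week fixed-dose period. After four small increases, subjects would stay at 2.85, 3.225 or 3.6 mg/week instead of 3.375, 3.75 or 4.125, or at 0.375, 0.45 or 0.525 mg/day instead of 0.45, 0.525 or 0.6. The sponsor may therefore limit the rule to weeks 4–16, since on that path one step at week 20 already gives a net cut of about 10–14%. That choice leaves uncovered the few subjects still below the limits at week 20.
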